9.3 Statistical analysis plan

These analyses will assess the efficacy and safety of BIC containing regimen in comparison with the boosted PI containing regimen.

All randomised patients who received at least 1 time any study treatment will be included in the intent-to-treat (ITT) analysis population. Of note patients lost-to follow-up or violating the protocol will not be excluded from the ITT population. Patients who switch treatment to another will be analysed as if they are remained in their initial randomisation group. All participants who are lost to follow-up or discontinued the study when they are endpoint free at time of leaving the study will be censored at the time of leaving the study. We will use time-to-event methods, including Kaplan–Meier survival curves and Cox proportional-hazards models to account for all participants in the analysis. The per-protocol population will include all patients from the ITT population except those who did not fulfil the inclusion/exclusion criteria, who withdrew their consent, gave up, lost to follow-up or discontinued early study medication for any reasons other than any component of the primary endpoint.

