3. STUDY METHODS

3.1 GENERAL STUDY DESIGN AND PLAN

LAPTOP study is an international, open-label, randomised, two arm, multicentre trial over 48 weeks to compare two strategies for HIV-1 infected patients with advanced disease.

Eligible patients will be randomised to receive either an integrated inhibitor containing regimen (B (50mg)/F (200mg)/TAF (25mg) [1 pill administered orally once daily for 48 weeks]) or a boosted PI regimen (D (800mg)/C (150mg)/F(200mg)/TAF (10mg) [1 pill administered orally once daily for 48 weeks]). Randomisation is stratified by country and baseline CD4 cell count (<50 cells/ μ L, 50-199 cells/ μ L, or \geq 200 cells/ μ L).

[figure not shown]

Figure 1: Study design

Study participants will be ART-naïve, HIV-1-infected individuals aged 18 or older who have at entry HIV viral load > 1000 copies/ml and at least one of the following: i) have AIDS with any CD4 cell count; ii) have severe bacterial infection (BI) and must have a CD4 cell count < 200/µl within 30 days prior to study entry; iii) are asymptomatic with CD4 cell count < 100/µL within 30 days prior to study entry; iv) are currently receiving treatment for OI. Women who were pregnant or breastfeeding or who declined a contraceptive method at screening were not eligible.

After the screening visit, participants will be seen at baseline, when they initiated c-ART and weeks 4, 8, 12, 24, 36 and 48, as well as a follow-up visit 30 days following the week 48 visit.

At each visit, participants will have routine safety monitoring as well as measurement of plasma HIV-1 RNA viral load, CD4, CD8 cells counts and a deep sequence resistance test. In the event of virological failure, local resistance tests should be performed on the first sample, and participants should discontinue study treatment and receive rescue therapy at the investigators' discretion.

Quality of life (QoL) questionnaire (EuroQoL EQ-5D-3L) and HIV Symptom Index (HIV-SI/SDM) questionnaire will be administrated at each visit from baseline.

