5.3 HANDLING OF MISSING DATA

The primary and all secondary end points will be analysed on a mITT basis.

During the study, participants may be lost to follow-up, withdraw or drop out. A participant will be considered lost to follow-up if he/she is unreachable for at least two consecutive visits by the study site until the end of the study. And so, for these participants, observations will be censored from the date of last observation.

In addition, for participants still being followed in the study but whose observation is missing at week 48 and at the 30-day visit after week 48, data will be censored at the last observation.

Partial dates will be extrapolated. For example, all dates saved as NK/FEB/2020 will be recoded as 15/FEB/2020 and those saved NK/NK/2020 will be recoded as 30/JUNE/2020. NK means not known.

For the assessment of HIV RNA viral load reduction at week 12, we will use the last observation carried forward approach to fill in missing data at visit 12.

For all continuous variables used as endpoint, if the value is missing at week 48 and the value at the 30-day visit after week 48 is not missing, it will be used to replace the missing week 48 value whether or not the patient has been switched off the study drug.

For participants who stop the study prematurely, if the Early Termination Visit (ETV) is performed, the value will be used to complete the nearest missing visit.

For participants for whom the date of onset of the clinical event used as an endpoint is missing, the missing date of onset will be replaced by the event reporting date.

For patients reported outcomes, we will used multiple imputation approach to fill in missing data.

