7.1 PRIMARY EFFICACY ANALYSIS

Endpoint

The primary endpoint is the first occurrence of any of the following components:

1. Virological failure
 - a) Insufficient virological response, either:
 - a. HIV-1 RNA reduction < 1 log 10 copies/mL at week 12, or
 - b. Viral load > 50 HIV-1 RNA copies/mL at week 48
 - b) Viral rebound, which is subsequently confirmed at the following scheduled or unscheduled visit, defined as either:
 - a. Rebound of HIV-1 RNA to >200 copies/mL after having achieved HIV-1 RNA <50 copies/mL
 - b. Rebound of HIV RNA by >1 log 10 copies/mL from nadir value, for patients whose viral load has never been suppressed below 50 copies/mL
2. Clinical events¹
 - a) Death related to HIV, AIDS, OI/severe BI or complications of therapy including IRIS
 - b) Any new or recurrent AIDS defining event on, or after 28 days of therapy
 - c) Any new serious non-AIDS defining event documented by the endpoint review committee (including severe BI, end stage liver disease, renal failure, cardiovascular event, and non-AIDS related malignant disease)
 - d) Clinically relevant AEs of any grade or IRIS which require treatment interruption (lasting > 5 days) of INI or boosted PI therapy within the first 48 weeks after randomisation. Discontinuation of BIC or boosted DRV followed by (within 5 days) continuation with another INI or PI, respectively, is not considered as a strategy failure or endpoint.

Descriptive statistics and graphical representation

The analyses will be performed with the mITT population and DPS1. Data will be summarized with the number and percentage of participants with an event. Kaplan-Meier curves will also be plotted for the primary endpoint and its component.

A table, listing for each participant any event, they may have had as well as the day from baseline to event onset, will be generated.

Statistical methodology

The proportion of patients with an event will be estimated using the Kaplan-Meier method. Episodes of clinical events diagnosed at baseline will not be considered as incident events in the study. For virological events evaluation data were censored at the time of treatment discontinuation.

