The follow-up will begin at baseline and continue until the week 48 visit, study discontinuation, loss to follow-up, or onset of the composite primary endpoint events; whichever occurs first. Participants lost to follow-up or who have discontinued the study when they are endpoint free at time of leaving the study will be censored at the date of last observation.

The effect of study treatment will be assessed using Cox regression model with treatment group and adjustments for stratification factor (country/group of neighbouring countries and baseline CD4 cell

counts ($<50/\mu\text{L}$ or $\geq50/\mu\text{L}$), as the sample size would not allow use of the stratification factors of randomisation (country and baseline CD4 in three categories (<50 ; $50-199$; $\geq200/\mu\text{L}$)). An adjusted hazard ratio (HR) and the associated 95% Confidence Interval (CI) will be calculated. Separate analyses for each component of the primary endpoint will be done. All P-values will be two-tailed with a significant level at 5%.

A sensitive analysis will be performed with the per-protocol population and DPS2.

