Virologic outcome will be determined by the last available measurement while the participant is on treatment and continues on trial within the time window. The time window for each timepoint is defined in Table A below.

Table A: Proposed Windows

Visit	Window (Through End-of-Study Week)	Window (Days)
24	18-30	127-210
36	30-42	211-294
48	42-54	295-378

Descriptive statistics and graphical representation

The analyses will be performed with the mITT population and DPS1. Data will be summarized with the number and percentage of participants with an event.

The proportion of patients with HIV-RNA viral load <50 copies/mL, HIV RNA viral load \geq 50 copies/mL, discontinuation due to Adverse Event (AE/SAE), discontinuation due to other reasons or on study but missing data at analysis time point will be calculated. The evolution over time will be analysed graphically using trend analysis.

HIV-RNA \geq 50 copies/mL includes: patients who changed any component of background therapy to a new drug class, changed background components that were not permitted per protocol, or changed any background drug in the regimen because of lack of efficacy (perceived or documented) before Week 48; patients who discontinued study drug or study before Week 48 for lack or loss of efficacy and patients who are equal to or above 50 copies/mL in the 48-week window.

AE/SAE includes: patients who discontinued because of adverse event (AE) or death at any time point from baseline through the time window if this resulted in no virologic data during the specified window.

Other Reasons includes: withdrew consent, loss to follow-up, moved, among others.

Statistical methodology

The proportion of patients with HIV-RNA viral load <50 copies/ml, HIV-RNA viral load \geq 50 copies/ml, discontinuation due to adverse event (AE/SAE), discontinuation due to other reasons or participating in the study but with missing data at the time of analysis will be calculated by dividing the number of participants with an event of interest by the total number of participants in the mITT population.

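### SAP 5.3 moves an Early Termination Visit value to the nearest missing visit at any distance, so values up to about 12 weeks early enter unwindowed analyses, and its precedence over the censoring in SAP 7.1 at week 48 is not stated

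*Combined protocol and SAP*

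**What the plan says.** SAP 5.3 deals with participants who stop the study prematurely: "if the Early Termination Visit (ETV) is performed, the value will be used to complete the nearest missing visit". It gives no maximum distance, no on-drug condition and no date for the filled value. SAP 3.1 schedules post-baseline visits at "weeks 4, 8, 12, 24, 36 and 48", each with a ±7-day tolerance (SAP 3.3).

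Other rules bear on the same value:

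- **Primary endpoint (SAP 7.1).** One failure component is "Viral load > 50 HIV-1 RNA copies/mL at week 48", with no day window. Follow-up is to "continue until the week 48 visit, study discontinuation, loss to follow-up" or the first primary event. Leavers who are "endpoint free at time of leaving the study will be censored at the date of last observation". Virological evaluation is censored when treatment is discontinued. Protocol 9.3 likewise says that those who "discontinued the study when they are endpoint free at time of leaving the study will be censored at the time of leaving the study".
- **Data set (SAP 5.2.1).** The data set for the primary and secondary endpoints (DPS1) keeps all observed data, including data after study drug is stopped.
- **Snapshot viral load (SAP 7.2.2).** "The time window for each timepoint is defined in Table A below": days 127-210, 211-294 and 295-378 for weeks 24, 36 and 48. The value must be taken on treatment and on trial. Table B (SAP 10.2.2) does the same for weeks 4, 8 and 12.
- **CD4 thresholds, CD4/CD8 ratio and laboratory values (SAP 7.2.5, 7.2.6, 10.1.6).** Time is categorical and no windows are given.
- **Other fills in SAP 5.3.** Patient-reported outcomes are multiply imputed. A missing week-12 viral load is filled by last observation carried forward.

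**The concern.** For a patient who attended every visit before leaving, the nearest missing visit is the next one, however far off it is. After week 12 that can be almost 12 weeks.

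In the unwindowed secondary analyses, a value taken just after week 12 can be analysed as week 24. CD4 and laboratory values are then credited with time on treatment that had not passed. If early leaving differs between arms, which is possible in an open-label trial, the error need not cancel.

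In the primary analysis the problem is an undecided outcome. Take a patient on study drug who attends week 36, leaves at week 37 and has 60 copies/mL at the early termination visit. Under 5.3 that value completes week 48 and the patient has failed. Under 7.1 follow-up ends at leaving, and an endpoint-free patient is censored. Whether the patient is endpoint free depends on whether 5.3 applies. Two statisticians could follow the plan and code this patient differently.

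**Working it through.** **1. The plan's own figures (SAP 4).** Margin: ln(0.63)/ln(0.75) = 1.606. Expected hazard ratio: ln(0.77)/ln(0.75) = 0.909. Events by Schoenfeld's formula (1:1, two-sided 5%, 80% power): 4 × (1.960 + 0.842)² / [ln(1.606/0.909)]² = 96.9, so 97. Evaluable patients: 97/0.24 = 404. With drop-out: 404/0.925 = 437, in line with 440. The stated figures reproduce and do not depend on this point.

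**2. How far a value can move.** Nominal visit days are 28, 56, 84, 168, 252 and 336.

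- Week 36 attended on day 252, early termination visit on day 253: 336 − 253 = 83 days early (11.9 weeks).
- Week 36 attended 7 days early (day 245), early termination visit on day 246: 336 − 246 = 90 days (12.9 weeks).
- The same distances hold for week 24 after week 12, and for week 36 after week 24.
- For weeks 4, 8 and 12 the largest early move is 27 days (34 with tolerance).
- Within the Table A windows the largest early move is 336 − 295 = 168 − 127 = 252 − 211 = 41 days (5.9 weeks).

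**3. How many patients.** Assume a constant drop-out hazard at 7.5% per year, all earlier visits attended, and an early termination visit for every leaver. With S(w) = 0.925^(w/52) and N = 440:

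- Leave by week 48: 440 × [1 − S(48)] = 30.6.
- Leave in weeks 36-48: 440 × [S(36) − S(48)] = 7.4. Of these, before day 295 (week 42.1): 440 × [S(36) − S(42.1)] = 3.8.
- Leave in weeks 12-24: 7.7. In weeks 24-36: 7.6. These matter only for the secondary analyses.

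| Drop-out per year | Leave in weeks 36-48 | Of these, before day 295 |
|---|---|---|
| 5% (assumed) | 5.0 | 2.6 |
| 7.5% (stated) | 7.4 | 3.8 |
| 15% (assumed) | 14.5 | 7.5 |

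**4. Extreme effect on the primary result.** Take the expected hazard ratio as the estimate. Its upper 95% limit is 0.909 × exp(1.96 × 2/√97) = 1.35. Now suppose that 7.7 leavers (a quarter of 30.6, slightly above the 7.4) all become week-48 failures and all are in the INI arm, where 202 × 0.23 = 46.5 events are expected. The hazard ratio becomes about 0.909 × (1 + 7.7/46.5) = 1.06. Its upper limit is about 1.06 × exp(1.96 × 2/√104.7) = 1.55, below 1.606.

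**The case against.** The strongest reply is that other rules already limit the damage. Much of it stands and sets the scope of the point.

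- **7.1 censors only endpoint-free leavers.** A patient counted as failing on the early termination value is not endpoint free, so 5.3 and 7.1 do not flatly contradict each other. This stands: the defect is unstated precedence.
- **Virological evaluation stops at treatment discontinuation.** This stands. It confines the week-48 problem to values taken while the patient is still on study drug. DPS1, which keeps later data, does not make this clearer.
- **Weeks 24 and 36.** A reader might infer that the clash with 7.1 extends to these visits. It does not: the primary endpoint has no threshold at either.
- **Unobserved successes.** A reader might infer that a value below 50 copies/mL creates a week-48 success. The endpoint that counts suppression is the snapshot, bounded by Table A. In the time-to-failure analysis a value below 50 creates no event.
- **Quality of life.** A reader might include it, but SAP 5.3 gives it its own multiple-imputation rule.
- **Unconfirmed failures.** The week-48 criterion needs no confirmation for any patient; confirmation applies only to rebound. The fill rule does not cause this.
- **Numbers.** Patients lost to follow-up are by definition unreachable, so not every leaver will have an early termination visit. The counts are upper bounds.

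None of this supplies a distance limit for the unwindowed secondary analyses, or says how to code the on-drug patient who leaves after week 36.

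**Conclusion.** The point holds in two places. First, the CD4 <200/<350, CD4/CD8 and laboratory analyses can receive values up to 83 days early (90 with tolerance). Second, the week-48 viral-load component of the primary endpoint is undecided for patients still on study drug who leave after attending week 36. At the stated drop-off that is at most about 7 of 440 patients, about 4 of them outside the SAP's own week-48 window. Only those with a value above 50 matter to the primary result.

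A reader might infer that the rule threatens the non-inferiority conclusion. At the stated drop-off the figures do not support that: even with about 8 extra failures, all in the INI arm, the upper limit is about 1.55. This reassurance belongs to the stated rate. The same approximation with all 14.5 leavers at 15% per year gives 0.909 × (1 + 14.5/46.5) = 1.19, with upper limit 1.19 × exp(1.96 × 2/√111.5) = 1.73. That needs twice the planned drop-off, every such leaver in one arm, and every one on drug with a value above 50. Nothing in the documents suggests it.

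The plan should be corrected before database lock. The likely effect on the primary result is small. The documents do not quantify how fast CD4 changes after week 12, so the size of the secondary bias is not known.

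**What to change.** Replace the sentence in SAP 5.3 with:

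> An ETV value is assigned to a scheduled visit only if its study day lies in that visit's window in Tables A and B and that visit has no value; otherwise it is not assigned to a visit.

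Add to SAP 7.1:

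> For the week-48 criterion of the primary endpoint an ETV viral load counts only if taken on days 295-378 and before treatment discontinuation, with the ETV date as the event date; other endpoint-free leavers are censored as in 7.1.

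Do not add a matching day 71-98 restriction for the week-12 criterion unless the week-12 carry-forward sentence in 5.3 is amended too. As it stands, that sentence would carry an earlier early termination value to week 12 anyway.

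The cost is SAP wording and a date check against windows already defined. SAP 5.1 allows the SAP to be updated before sign-off. Three limits should be accepted openly:

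- A value up to 41 days early can still count as week 48.
- Some later values become missing. These include early termination visits on days 99-126, which fall between the end of Table B (day 98) and the start of Table A (day 127).
- The mixed models for CD4/CD8 and laboratory values can use incomplete follow-up. The independence GEE for CD4 <200 and <350 is less protected if missingness depends on earlier CD4.

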5.4 INTERIM ANALYSIS

No interim analysis for efficacy was planned. However, an independent data monitoring committee (DSMB) consisting of independent scientists not otherwise involved in the trial has been appointed and has reviewed the data regularly during the study for safety and scientific integrity and has made recommendations to the sponsor.

However, in the event of external evidence of trial interventions, the sponsor may seek advice from the DSMB and the DSMB could recommend an interim efficacy analysis based on the observed data collected at that time to help make a recommendation. A two-sided Type-I error rate of 5% will be used because no formal interim analysis for efficacy is planned.

5.5 MULTIPLE TESTING

Because all subgroup analyses are designed to detect possible heterogeneity of the treatment effect across subgroups, and because they are exploratory and supportive, no adjustment for multiplicity is necessary.

6. SUMMARY OF STUDY DATA

All continuous variables will be summarised using the following descriptive statistics: n (non-missing sample size), mean, standard deviation (SD), 1st quartile, median, 3rd quartile, maximum and minimum. The frequency and percentages (based on the non-missing sample size) of observed levels will be reported for all categorical variables.

The number of patients and the flowchart of the study will be presented. The period of enrolment and the total number of patients screened to be included in the study will be presented. The number of ineligible patients and the total number of randomised patients will be presented. The number of patients who never take the study treatment will also be presented by group and those who remained on the study treatment up to week 48 will be presented.

6.1 SUBJECT DISPOSITION

The number of participants and the flowchart of the study will be presented as in the CONSORT flowchart (Figure 2).

[figure not shown]

Figure 2: CONSORT flowchart

For the analysis, a summary table with the description of the number of included subjects, the number of randomized subjects, the number of subjects in whom the treatment was initiated, the number of subjects in whom the treatment was not initiated and reasons, the number of subjects who discontinued the study and reasons and when, the number of subjects analyzed, and the number of subjects excluded from the analysis and reasons, will be prepared by treatment group. The dates of the inclusion period will be reported as well as the date of the last follow-up visit. The median (IQR) duration of participation and the total number of person-years will also be reported. The person-year is the total sum of the number of years that each subject of the study population has been under observation. The duration of participation in years for each subject will be calculated by the difference between the date of the last observation and the date of randomization divided by 365.25.

6.2 PROTOCOL DEVIATIONS

The following deviations are defined for the purpose of analysis:

- Did not fulfil the eligibility criteria
- Interruption of study treatment for >10% of total time on treatment
- Received treatment from another randomisation group
- Consent withdrawal
- Lost to follow-up (at least 2 consecutive visits missed until the end of the study)
- At least one missed follow-up visits for those not lost to follow-up

At least one visit for which the viral load is missing for those for whom all visits have been madeA summary table by treatment group and overall with the number and percentage of subjects presenting deviations will be prepared for the subjects in the mITT population.

6.3 DEMOGRAPHICS AND OTHER BASELINE CHARACTERISTICS

The summary of the demographic and baseline characteristics will be performed on the mITT population. The data will be summarized overall and by randomisation arm (Integrase inhibitor (BIC) versus protease inhibitor (DRV/c)). Baseline data corresponds to all data collected prior to the initiation of the study interventions.

6.3.1 Descriptive statistics

Demographics and baseline characteristics will be summarized as follows:

- For continuous variables: sample size, mean, standard deviation, median, interquartile range, minimum and maximum.
- For categorical variables: sample size, proportion and number of patients in different categories.

